Aim 1: Use rtfMRI-NF and motor imagery to train CA participants to improve motor accuracy.

- Aim 1.1: Train CA participants (N=30) to engage neural regions during motor imagery that are associated with overt finger tapping at slow (1 Hz) and fast (4 Hz) speeds.
- *Aim 1.2:* Correlate motor imagery skill (i.e., slider bar distance from target) with overt tapping performance.

• *Aim 1.3:* Evaluate the relations between overt tapping accuracy and neurological symptoms as well as motor imagery skill with offline assessments of motor imagery ability.

Aim 1 will use rtfMRI-NF during motor imagery to train CA participants to improve motor accuracy. Thirty CA participants will receive NF during motor imagery in an experiment in which we hypothesize that 1) CA participants will be able to control a NF interface; 2) imagery skill will be positively correlated to improvements in overt tapping accuracy; and 3) overt tapping accuracy will correlate with neurological signs, whereas motor imagery skill will correlate with assessed motor imagery ability.

Aim 2: Translate rtfMRI-NF learning into at-home therapy strategies for continued training.

- Aim 2.1: Examine whether motor imagery strategies from rtfMRI-NF training translate into successful at-home therapy training
- *Aim 2.2:* Compare motor imagery performance during rtfMRI NF with at-home motor imagery benefits.

Aim 2 will translate rtfMRI-NF learning into at-home therapy strategies for three weeks of continued training in which we hypothesize that 1) continued practice with imagery strategies will lead to additional improvements in motor timing and precision, and 2) performance during rtfMRI-NF training will positively correlate with at-home motor imagery performance.

Exploratory

Aim 3: Design next-generation approaches to rtfMRI-NF. The data from Aim 1 will be analyzed to optimize the future rtfMRI experiments in the CA population. We will examine whether the NF session can be streamlined to deliver more accurate NF in shorter sessions. To enable future studies to operate within an experimental medicine frame work we will examine three major questions. Aim 3.1 Are there group differences in CA versus healthy controls? Aim 3.2 Are healthy models of motor imagery viable for CA participant NF? Aim 3.3 Can the NF session be streamlined to deliver more accurate NF in more efficient sessions?

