When the neuropsychological testing portion of the visit is completed, they will then be trained on a cognitive task that will be administered inside the MRI. If they are a woman of childbearing age, they will be given a urine drug pregnancy test. If the pregnancy test is positive, they will be removed from the study and PHI and any data collected thus far will be destroyed. After training and pregnancy test if needed, they will be escorted to the F.M. Kirby Research Center across the street, which houses the MRI scanner. Participants will be asked to arrive 1 hour before the MRI scan is scheduled to begin. Total time spent in the scanner will be approximately < 1 hour, and

Task	Approximate Time (minutes)
Training on cognitive test (outside the scanner beforehand)	10
MPRAGE	6
Overt tapping	12
Motor imagery	12
Overt tapping	12

we will reserve 1 full hour to allow time to get in and out of the scanner for this movement disordered population.

Participants will perform an overt tapping test as a baseline measure of online task performance. Therapy begins the next day and lasts for 21 days (participants complete at least 5 days per week to accommodate scheduling conflicts). A final measure of overt tapping will be performed the day after therapy ends. Participants will be randomly assigned to one of three training conditions. Group 1, imagery only; Group 2, overt tapping only; and Group 3, imagery plus overt tapping. During imagery, participants will view the task while imagining that they are finger tapping in time with the flashing cursor, using the imagery strategies identified during their rtfMRI-NF session. During overt tapping, participants will finger tap in time with the flashing cue.

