Participants will be instructed to find a quiet room with minimal distractions and remain in a comfortable seated position with their hands resting on the keyboard. All tests include blocks of trials in which either 1 or 4 Hz cues are presented. In the baseline and final measures, a session will consist of one 4-minute test comprised of 12 blocks; each frequency will be presented six times. In the 3-week therapy component, a session will consist of two 2-minute tests comprised of six blocks each; each frequency will be presented three times per block. In all sessions, frequency blocks will be pseudorandomized such that the first block will always be the 1 Hz frequency, and the same frequency will be presented in no more than three consecutive blocks. All blocks begin with 5 seconds of rest, followed by 15 seconds of the flashing cue. After completion of their experience for the day (e.g, vividness of imagery, perceived tapping precision, etc.).

	BASELINE M	EASURE	3 WEEKS OF AT-HOME THERAPY CONDITIONS				FINAL MEASURE	
	Overt tapping (4 min)	Daily log (3 min)	Imagery (4 min)	Overt tapping (4 min)	Imagery + overt tapping (2 + 2 min)	Daily log (3 min)	Overt tapping (4 min)	Daily log (3 min)
Group 1 (n=10)	X	X	X			X	X	X
Group 2 (n=10)	X	X		X		X	X	X
Group 3 (n=10)	X	X			X	X	X	X

b. Study duration and number of study visits required of research participants.

Each participant will have 1 in-person study visit (day 1) that will take about 3-4 hours. Days 2-23 of the study will consist of at-home therapy 5x weekly that may take up to 10 minutes to complete. At-home therapy includes a baseline online measure and log (7 minutes), group designated tasks (See table below) and log (7 minutes), and a final online measure and log (7 minutes). The total duration of the study is 2 years of data collection and analyses (allowing up to 3 additional years of data analyses).

General Study Protocol					
Event	Tasks Completed	Duration			
Screening	Clinical appropriateness	15-20 minutes			
(phone)					
	Consent*, pre-MRI pregnancy test	25-30 minutes			
Screening					
(In-person)					
In-person	Task orientation	10-15 minutes			
visit	MRI: Anatomical scan and rtfMRI-NF	1 hour (42 min			
		active MRI)			
	Questionnaires*, assessments*, neurological exam, at-home	2 hours			
	instructions				
At-home	Baseline online measure & log	7 minutes			
therapy	Training according to group assignment: Group 1 = motor	7 minutes per			

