2) At-home overt tapping accuracy improvements will be analyzed by comparing the mean accuracy on overt tapping between baseline and final measures at home (pre- and post- 3-week at-home therapy training) to compute a delta measure that will indicate magnitude of accuracy improvement at each frequency (1 and 4 Hz). This will be analyzed using paired t-tests within frequency conditions. As a follow-up analysis of improvement during the 3-week therapy (for training Groups 2 and 3 who perform daily overt tapping exercises), the mean accuracy of overt tapping at both frequencies will be measured for each session and compared using repeated measures ANOVAs and post-hoc t-tests as appropriate.

b. Secondary outcome variables.

1) The relation between imagery accuracy and tapping accuracy with supplemental assessments of imagery and motor symptoms will be analyzed using non-parametric correlation tests, such as Spearman's rank-order correlation coefficient test, because of the ordinal values in the KVIQ and ICARS assessments. Mean imagery accuracy and tapping accuracy scores from the final MRI assessment will be compared separately to the KVIA an ICARS.

2) The relation between brain activity during imagery NF and overt tapping improvements will be analyzed using Pearson correlations between the mean of region of interest activity (minus rest) during NF training and the RSME delta scores.

3) The influence of ancillary measures on overt tapping and motor imagery accuracy will be analyzed using non-parametric correlation tests (e.g., Spearman's rank) because of the ordinal values in the HAM-A, HAM-D, CCAS, and WRAT assessments. Mean imagery accuracy and tapping accuracy scores from the final MRI assessment will be compared separately to each of the assessments.

c. Statistical plan including sample size justification and interim data analysis.

We plan to enroll 30 participants in this study. The sample size was determined through a power analyses using G*Power 3.1.9.2 software [40]. Because motor imagery, with or without rtfMRI-NF, has never been used as a treatment approach for people with cerebellar ataxia (CA), as proposed here, our power analyses are extrapolated from information we have obtained that in three prior studies that support the premise and feasibility of Aim 1, which is to use rtfMRI-NF and motor imagery to train CA participants to improve motor accuracy.

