In general, comparisons between measures with continuous variables (e.g., accuracy) within participants will be conducted using paired-tests, repeated-measures ANOVAs, and post-hoc t-tests as appropriate. Pearson correlations will be run between continuous variables (e.g., motor imagery accuracy and delta scores). Non-parametric tests will be used when assessments that with ordinal values (ICARS, KVIQ, mood, and cognitive ancillary measures) are included.

d. Early stopping rules. N/A

8. Risks

a. Medical risks, listing all procedures, their major and minor risks and expected frequency.

Risks/Benefits

The following relevant risk/benefit considerations and potential ethical issues may arise as part of the proposed study. Any adverse events will be promptly reported to the IRB. As this is not an intervention study, participants will be informed as part of the consent process that their medical care will not be affected or altered by their decision to participate in this research. There are no financial risks to the participant.

MRI: Screening of participants will consist of checks for contraindications to MRI scanning. Urine pregnancy testing will be conducted on-site for women of child bearing age. Currently pregnant participants will be excluded. There are no known significant risks for an MRI exam. Subjects, may, however, experience mild discomfort by the noise made by the magnet during the procedure, bothered by feelings of claustrophobia, or anxiety. There is a risk that the subject may become bored or fatigued with cognitive testing while in the scanner.

EMG: The EMG will be utilized to determine whether participants are moving their finger muscles during the imagery condition in the MRI scanner, in which they are not supposed to do so. To apply the surface electrodes on the participant's arm, skin prepping gel similar to a gentle exfoliating cream will first be applied and rubbed onto the participant's skin in order to remove any dead skin. There is a risk that subjects may not like the feeling of the cream or that their skin will become slightly irritated. The risks of the electrodes are the same as those of applying a band-aid on someone's arm: subjects may be uncomfortable with the adhesive feeling of the electrodes, and the electrodes might feel similar to ripping off a band-aid when taken off.

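### The follow-up analysis of improvement during home therapy is an order-blind session ANOVA; a pre-specified trend over therapy day would be a cheap improvement of minor importance

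*Combined protocol and SAP*

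**What the plan says.** Section 7a, item 2 makes the main at-home analysis a paired t-test of baseline against final overt tapping, per frequency. It then adds a second analysis, introduced by "As a follow-up analysis of improvement during the 3-week therapy" and limited to two arms: "for training Groups 2 and 3 who perform daily overt tapping exercises". The method is that "the mean accuracy of overt tapping at both frequencies will be measured for each session and compared using repeated measures ANOVAs", with post-hoc t-tests where suitable.

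The general methods statement in section 7c adds only that comparisons "within participants will be conducted using paired-tests, repeated-measures ANOVAs, and post-hoc t-tests as appropriate". Neither place names a trend contrast, a slope, a mixed model, a sphericity correction, the post-hoc pairs, or a rule for unequal session counts.

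On session counts, section 4a has therapy last 21 days, where "participants complete at least 5 days per week to accommodate scheduling conflicts". Section 4b says "Days 2-23 of the study will consist of at-home therapy 5x weekly". The table in section 4a gives 10 people per group. Group 2 taps for 4 minutes a session, and Group 3 taps for 2 minutes after 2 minutes of imagery.

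**The concern.** Improvement is a question about order and direction. A session-factor F has neither: shuffling or reversing the sessions leaves it unchanged. It spreads any steady gain over 14 or more numerator degrees of freedom, and a significant result could reflect worsening or fluctuation. The post-hoc t-tests do not settle this, because the pairs are left open and there are many of them.

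The classical ANOVA also needs a value for every person at every session level. The plan permits different counts and does not say how sessions are to be lined up.

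The risk is that a modest real gain during therapy is missed, or that a significant F is read as improvement when it does not show that. Section 7c also says that the data will feed power calculations for later grants. A slope with its between-person SD serves that use more directly than an omnibus F.

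**Working it through.** **No figure to reproduce.** The plan states no power, effect size or SD for this analysis; section 7c says that the power work targeted Aim 1. Everything below other than the counts is an assumption.

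**Counts from the documents.** Sessions per person: 3 × 5 = 15 up to 3 × 7 = 21. Numerator df for session: 14 to 20. Possible post-hoc pairs per frequency: 15 × 14 / 2 = 105 up to 21 × 20 / 2 = 210.

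**Why one df helps.** Take n = 20, k = 15 sessions, independent errors, and a linear change D from first to last session in single-session within-person SDs. The noncentrality is λ = n · D² · k(k+1) / [12(k−1)]. With D = 0.5, λ = 20 × 0.25 × (15 × 16)/(12 × 14) = 20 × 0.25 × 1.429 = 7.14. The omnibus F on 14 and 19 × 14 = 266 df then has 32% power. The linear contrast, with the same λ on 1 and 19 df, has 72%. For one group of 10 with D = 0.75, λ = 10 × 0.5625 × 1.429 = 8.04, and the figures are 34% and 71%.

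**A fuller simulation.** Assumptions: one frequency, total SD 1, change 0.5 SD, within-person correlation 0.6 (mean error variance 0.4), slope SD 0.3, and five random days in each of three weeks. Group 3's error variance is twice Group 2's; equal variances hardly change the results. Change is either linear or a plateau, (1−e^(−(day−1)/τ))/(1−e^(−20/τ)). Here 0.5 total SD is 0.5/√0.4 = 0.79 within-person SD, so power is higher than in the first case above. Approximate power (%), n = 20 pooled:

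| Errors | Change | Huynh-Feldt ANOVA | Linear-day slope | Log-day slope |
|---|---|---|---|---|
| Independent | Linear | 69 | 92 | 90 |
| Independent | τ = 4 days | 58 | 80 | 87 |
| Independent | τ = 2 days | 44 | 54 | 71 |
| Independent | τ = 1 day | 32 | 30 | 49 |
| AR(1) = 0.5 | Linear | 60 | 73 | 70 |
| AR(1) = 0.5 | τ = 2 days | 41 | 32 | 49 |
| AR(1) = 0.5 | τ = 1 day | 31 | 18 | 31 |

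Within one group of 10, independent errors, Huynh-Feldt ANOVA against log slope: about 33 vs 58% (linear) and 21 vs 39% (τ = 2 days). Simulation error is about 2 to 3 points.

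**Type I error.** With AR(1) = 0.5 the uncorrected ANOVA rejects a true null about 7.5% of the time, Huynh-Feldt 5.4%, and the slopes 4.5 to 4.8%.

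**Sensitivity to effect size.** With independent errors, n = 20 and linear change, uncorrected ANOVA against log slope is 27 vs 50% for a change of 0.3 SD, and 99 vs 100% for 0.8 SD.

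**Where a trend loses.** With independent errors, a step in week 3 gives log slope 93% and uncorrected ANOVA 97%. A gain that has reversed by day 21 gives linear slope 5%, log slope 18% and uncorrected ANOVA 69%.

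**The case against.** The strongest reply is that the directional question already has a one-df test. The main at-home analysis is the paired t-test of baseline against final. The session ANOVA is only a follow-up, no stated power rests on it, and section 7c concedes that some comparisons may be underpowered. All of that stands, and it limits the importance of the point. It does not make the follow-up test fit the question that it is given.

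A second reply is that the gain from a trend depends on an unknown learning shape. This also stands. With autocorrelation, which is plausible for near-daily measurements, the linear-day slope does not merely lose its lead when learning is early. It falls clearly below the corrected ANOVA (about 32 vs 41% and 18 vs 31%). The log-day slope held level or better in the linear and plateau cases above, but not in the week-3 step or the reversed gain.

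Third, a reader might infer that sections 4a and 4b contradict each other on frequency. They do not have to: five a week can be read as the minimum. What remains is that a minimum permits unequal counts and no alignment rule is given. Aligning by session number over the first 15 would balance everyone who meets the minimum.

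Fourth, a reader might infer that the Aim 2 hypothesis in section 2 goes untested. That hypothesis is that "continued practice with imagery strategies will lead to additional improvements in motor timing and precision". It concerns imagery, and Group 2 does no imagery during therapy, so it lends no support here.

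**Conclusion.** The point holds as a cheap improvement of minor importance. The stated question is improvement, the stated test is blind to order and direction, and its data layout is not guaranteed by the schedule.

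The advantage of a log-day trend over a Huynh-Feldt ANOVA is about 21 points for linear change (90 − 69) with 20 people pooled and independent errors. It is about 25 points (58 − 33) within one group of 10. Under AR(1) = 0.5 with 20 people it is about 10 points (70 − 60), falling to nothing for a 1-day plateau. The pooled figures should not be taken as the expected power, because section 7a does not say that the two groups are combined. Every size depends on the assumed change, correlation, slope SD and shape.

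The documents do not support a broader conclusion that the at-home result is compromised, since the baseline-versus-final paired t-test is untouched. Nor do the calculations show that a trend test is better whatever the course of learning.

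**What to change.** In section 7a, item 2, pre-specify within each frequency a one-df trend over therapy day (1 to 21) as the main follow-up test, using every completed session. Either of two forms will do:

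- per-person slopes of tapping error on log(therapy day), with their mean tested against zero; or
- a mixed model with random intercept and random slope on log(therapy day).

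In either form, include a term for Group 2 versus Group 3 and report each group's slope. State whether the main test averages over the groups. Report linear day as a sensitivity analysis.

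Keep the repeated-measures ANOVA as a supporting test of any session difference, with a sphericity correction such as Huynh-Feldt and sessions aligned by number over the first 15. Say how people with fewer than 15 sessions are handled.

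The cost is a few sentences of plan wording and standard software, with no change to data collection. The price of the trend test is that it assumes a shape: it can miss a gain that later reverses, and the linear-day form can do worse than the ANOVA when learning is early. That is why the ANOVA should stay.

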Exclusion criteria: History of Axis I psychiatric disorders (including alcohol and drug dependence), severe or unstable medical disorder, non-ataxia related neurological disorders, such as stroke or epilepsy, history of head injury that resulted in a loss of consciousness greater than 5 minutes and/or neurological sequelae, any condition that is contraindicated for the MRI environment (e.g., metal in the body, pacemaker, claustrophobia), or currently pregnant, and clinical diagnosis of multiple system atrophy (MSA, due to the disruption of the central autonomic network) or Friedrich's ataxia (FA, due to extensive involvement of the spinal cord and loss of sensory fibers in the peripheral nerves). MSA and FA differ substantially from other forms of CA and would greatly complicate interpretation of the data. Eligible subjects may be asked to refrain from medications that affect the central nervous system that would also make data difficult to interpret (e.g., sedatives) for an appropriate period of time prior to scanning. Participants will be excluded if they do not have a home computer with internet available to complete the 3-week at-home component of the study protocol.

6. Drugs/ Substances/ Devices

- a. The rationale for choosing the drug and dose or for choosing the device to be used.
- N/A
- b. Justification and safety information if FDA approved drugs will be administered for non-FDA approved indications or if doses or routes of administration or participant populations are changed.
- N/A
- c. Justification and safety information if non-FDA approved drugs without an IND will be administered.

N/A

7. Study Statistics

a. Primary outcome variable.

1) Overt tapping accuracy improvements will be analyzed by comparing the mean accuracy on overt tapping between baseline and final measures (pre- and post- NF) to compute a delta

measure that will indicate magnitude of accuracy improvement at each frequency (1 and 4 Hz). This will be analyzed using paired t-tests within frequency conditions.

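### The severity correlation in section 7b appears to use the tapping run after neurofeedback, which mixes impairment with response to training; name the pre-neurofeedback run instead

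*Combined protocol and SAP*

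**What the plan says.** Section 7b sets the score for the secondary correlations. Item 1, for the imagery questionnaire (printed KVIA, read here as KVIQ) and the ICARS, states: "Mean imagery accuracy and tapping accuracy scores from the final MRI assessment will be compared separately to the KVIA an ICARS". Item 3, for HAM-A, HAM-D, CCAS and WRAT, states: "Mean imagery accuracy and tapping accuracy scores from the final MRI assessment will be compared separately to each of the assessments". Both use Spearman-type tests. No significance level, sidedness, expected coefficient or power is given for these correlations.

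Other sections show what this rule most naturally selects:

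- Section 7a item 1 describes the scanner outcome as "comparing the mean accuracy on overt tapping between baseline and final measures (pre- and post- NF) to compute a delta". Baseline is thus paired with pre-NF and final with post-NF.
- The scan table in section 4a lists the row "Overt tapping 12" twice, with one 12-minute motor imagery run between the two.
- Section 4b states: "Each participant will have 1 in-person study visit (day 1) that will take about 3-4 hours". There is no later MRI visit that the word final could mean.

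The hypothesis in section 2, Aim 1 is that "overt tapping accuracy will correlate with neurological signs, whereas motor imagery skill will correlate with assessed motor imagery ability". The same paragraph expects that "imagery skill will be positively correlated to improvements in overt tapping accuracy".

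**The concern.** The Aim 1.3 hypothesis on neurological signs is most directly about status: do people with worse ataxia tap less accurately? A score taken after NF is the starting level minus whatever that person gained. The trial's own hypothesis is that gains differ between people, in line with imagery skill. The post-NF score therefore carries variation that comes from training response. It also carries any practice or fatigue effect from the earlier runs.

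Section 4a places the neuropsychological battery, which includes the ICARS, before task training and the scan. A severity rating made before training would then be paired with a tapping score made after it. (The table in section 4b lists the assessments below the MRI row, but does not say that this is the order.)

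At stake is how a secondary result can be read. A weak correlation might reflect uneven gains, and a strong one might reflect severe participants gaining less. Neither could be read cleanly as a relation between impairment and tapping. No reason is given for preferring the post-NF run, and no analysis of the pre-NF run against the ICARS is planned.

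**Working it through.** **Which run is meant.** The scan order is tapping, imagery, tapping, in a single visit, and section 7a pairs baseline and final with pre- and post-NF. The final scanner tapping score is therefore the second tapping run. For imagery there is only one run, given under NF and placed before the last tapping run. The word final selects nothing for imagery, and read literally it points to a run without imagery.

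**Is there a figure to reproduce?** No. The Background reports that higher ICARS went with slower tapping and greater error, on a tapping task without NF, but gives no coefficient. Everything below is an illustration on assumed inputs.

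**Model.** Work with tapping error, with pre-NF SD set to 1, and let post-NF error = pre-NF error − gain. Define:

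- ρ = correlation of pre-NF error with ICARS
- k = SD of gain divided by SD of pre-NF error
- g = correlation of gain with pre-NF error
- h = correlation of gain with ICARS

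Then r_post = (ρ − k·h) / √(1 + k² − 2·k·g).

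Power uses the Fisher z approximation (Pearson, standing in for Spearman) at the planned n = 30, two-sided 0.05 assumed: Φ(atanh(r)·√27 − 1.96).

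**Pre-NF run, ρ = 0.50:** atanh(0.50) = 0.549; 0.549 × 5.196 − 1.96 = 0.89; power about 81%.

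**Post-NF run, ρ = 0.50, k = 0.5:**

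- Gain unrelated to severity (g = h = 0): 0.50/√1.25 = 0.447; power about 71%.
- More severe participants gain more (g = h = 0.3): (0.50 − 0.15)/√0.95 = 0.359; power about 50%.
- More severe participants gain less (g = 0, h = −0.3): (0.50 + 0.15)/√1.25 = 0.581; power about 93%. If g is also set to −0.3, the denominator becomes √1.55 and r is 0.65/1.245 = 0.52 (power about 85%): still inflated, but less so.

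**Small gains, k = 0.25, unrelated to severity:** 0.50/√1.0625 = 0.485; power about 79%. This is a negligible change.

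**Range over the assumed ρ (k = 0.5), correlation and power:**

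| ρ (pre-NF) | Pre-NF power | Gain unrelated | Severe gain more (g = h = 0.3) | Severe gain less (g = 0, h = −0.3) |
|---|---|---|---|---|
| 0.40 | 60% | 0.36, 49% | 0.26, 28% | 0.49, 80% |
| 0.50 | 81% | 0.45, 71% | 0.36, 50% | 0.58, 93% |
| 0.60 | 95% | 0.54, 88% | 0.46, 74% | 0.67, 99% |

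**No association before NF (ρ = 0, g = 0).** With h = −0.3 and k = 0.5, r_post = 0.15/√1.25 = 0.13. For k from 0.25 to 0.75 it runs from about 0.07 to 0.18. A modest correlation can thus arise from training response alone.

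**The case against.** The strongest reply is that the term is undefined. One phrase governs both imagery and tapping scores, and it cannot be taken literally for imagery. It might loosely mean the MRI session as opposed to the at-home final measure. That stands as a caution: the post-NF reading is an inference, though sections 4a, 4b and 7a all support it and nothing in the text supports the pre-NF run. On either reading, the run needs naming.

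Second, the pre-NF run may not be cleaner. It is the first run in the scanner, after only 10 minutes of practice outside, so it is untrained only in the sense of being before NF. Independent familiarisation noise with SD 0.5 would cost as much as an unrelated gain of that SD (0.50/√1.25 = 0.447). This also stands, and is why the post-NF run should still be reported.

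Third, Aim 1.3 does not say that tapping must be untrained, and item 3 is about the influence of mood and cognition, for which performance after training is a legitimate target. That stands for item 3. The neurological-signs hypothesis does not reach those measures, so the documents do not support declaring the post-NF run wrong there.

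Fourth, the stakes are modest. These correlations are secondary and outside the power justification. Section 7c concedes that the sample may be too small for some comparisons, the primary deltas are untouched, and both runs are collected anyway.

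**Conclusion.** The point holds as a low-cost improvement to a secondary analysis. As written, the rule most naturally pairs the ICARS with the post-NF tapping run. That mixes impairment with response to NF, practice and fatigue when a pre-NF score from the same session is available.

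A reader might infer that the choice must weaken the severity correlation, so that a null result would be an artefact and a definite amount of power is lost. The documents do not support that. They give no correlation with the ICARS, no spread of gains and no relation of gains to severity. The effect can go either way: from an assumed 0.50, to about 0.36 or about 0.58 with gain SD 0.5, and to about 0.49 if gains are small and unrelated to severity. The Background's remark that 4 Hz may be near these participants' tapping limit makes smaller gains in severe participants plausible at that rate, which would inflate the correlation. What can be said is that the score is contaminated, with direction and size unknown.

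**What to change.** In section 7b item 1:

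- Name the pre-NF scanner tapping run as the score correlated with the ICARS.
- Name the single NF imagery run as the imagery score, including for the KVIQ.
- Report the post-NF tapping run against the ICARS as a sensitivity analysis.
- If response to training is of interest, correlate the tapping delta with the ICARS as a separate analysis.

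In item 3, state which tapping run is used, and report the pre-NF run for HAM-A, HAM-D, CCAS and WRAT alongside the post-NF run.

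The change is wording only. Both runs are already collected, so it adds no scan time or burden for participants. The costs are a few more secondary correlations to report, and some possible familiarisation noise in the first run. Fixing the run in advance also prevents a choice made after the results are seen.
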